Intolerable nausea or vomiting	First	Study drug may be withheld and then restarted at a reduced dose by skipping one of the doses.

AE	Occurrence ^b	Action
	Second	Discontinue study drug permanently if the intolerance reoccurs or persists.
QTcF >500 ms for female subject OR >480 ms for male subject, at any time point	-	
The ECG should be repeated as triplicate (all three within 2 minutes) and a cardiology consult may be obtained as medically necessary.
 
 • If the repeat ECG confirms QTcF >500 ms (females) or >480 ms (males), dosing must be interrupted for up to 14 days • If the QTcF resolves to ≤480 ms (males and females)/they may resume dosing at the reduced dose by skipping one of the doses (ie, morning or evening) • If the QTcF remains >480 ms (males and females) after 14 days of dose interruption, the study drug must be permanently discontinued.
QTcF change of >30 ms from baseline	-	If the QTcF has increased >30 ms when compared to the baseline with no other known etiology, and the PI considers it clinically significant then a confirmatory ECG (single) will be performed and dose should be reduced by skipping one of the doses (ie, morning or evening) for the remainder of the study.

Abbreviations: ACE, angiotensin-converting-enzyme; AE, adverse event; ALP, alkaline phosphatase; ALT, alanine aminotransferase; ANC, absolute neutrophil count; AST, aspartate aminotransferase; csDMARDs, conventional synthetic disease-modifying antirheumatic drugs; ECG, electrocardiogram; MOA, mechanism of action; PI, principal investigator; QTcF, QT interval correction for heart rate (QTc) using Fridericia's correction formula; ULN, upper limit of normal

- ^a These are examples based on previously observed AEs for agents with similar MOA (ie, fostamatinib). All other potential/spontaneous Grade 3/4 AEs that can warrant dose reduction or interruption are not excluded and will be assessed on an ongoing basis during the study. Those would be evaluated upon judgment by the principal Investigator and the safety operations team.
- ^b First/second occurrence relates to AE; abnormalities at repeat tests during monitoring of an AE are considered to belong to the same event (AE).
- c A central laboratory must be used for repeat ALT, AST, ALP or ANC.

Subject Error

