Abbreviations: ACR, American College of Rheumatology; CD63, cluster of differentiation 63; DAS, disease activity score; EDTA, ethylenediaminetetraacetic acid; EOS, end-of-study; EOT, end of treatment; FSH, follicle-stimulating hormone; HBsAg, hepatitis B surface antigen; HIV, human immunodeficiency virus; HAQ-DI, Health assessment questionnaire disability index; HBcAb, hepatitis B core antibody; HCV, hepatitis C virus; hsCRP, high sensitivity C-reactive protein; PD, pharmacodynamic; PK, pharmacokinetic; PPD, purified protein derivative; RA, rheumatoid arthritis; TB, tuberculosis; WOCBP, women of child bearing potential.

^a When procedures overlap at the same timepoints, the vital parameters assessment will be performed first followed by laboratory parameters and other procedures (Section 6.4.2).

^b Subject who choose to discontinue study treatment, but continue to participate in the study should complete EOT visit as soon possible, preferably within 2 weeks. Afterwards, subjects should follow the regular visit schedule and adhere to all study procedures except for dispensing study drug, and blood sample collection for optional exploratory research and validation studies.

^c Any of the procedures may be performed at an unscheduled visit at the discretion of the investigator.

^d All study procedures on Day 1 must be completed prior to randomization in order to save time for IMP dispensation and postdose PK/PD sampling.

^e A complete physical examination should be performed at the time points specified. Interim physical examinations can be performed at the discretion of the investigator, if deemed necessary to evaluate AEs or clinical laboratory abnormalities (Section 6.4.1).

^f Vital sign measurements include systolic and diastolic blood pressure, pulse rate, respiratory rate, and oral temperature (tympanic temperature for Korean subjects). The subject must be seated for 5 minutes before all measurements are taken (Section 6.4.2).

^g Patient questionnaires and scales should be performed prior to any procedures and assessments. The HAQ-DI should be scored for all 8 categories (Section 6.3.3).

^h TB testing will be performed for all subjects within 28 days of Day 1. Positive diagnostic TB test, which is defined as positive QuantiFERON Gold test will be tested in central laboratories for all subjects and will determine subject's eligibility with regards to TB.

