4.2. Baseline Definition and Visit Window

Baseline value is defined as the last non-missing value on or before the date of the first dose of study drug. For subjects who were not treated, the baseline will be the assessment value taken on the screening visit, on or before the randomization day.

There is no separated visit folder designed in EDC for the treatment early terminated visit and the visit folder 'Visit 5 EOT' will serve as both the visit at Week 12 and the early terminated visit. Therefore, the assessments captured under visit folder 'Visit 5 EOT' will be summarized under visit Week 12 only when the subjects completed the treatment period; otherwise, 'Visit 5 EOT' will be treated as the treatment early terminated visit. There is no other visit mapping

performed and all the by-visit summaries will be based on the nominal visit as collected on the eCRF page except the visit handling of ‘Visit 5 EOT’.

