9.3. Clinical Laboratory Evaluations

The laboratory values will be graded using National Cancer Institute's Common Terminology Criteria for Adverse Events (CTCAE) version 5.0. For hematologic and chemistry laboratory values that fall outside of the grade criteria of CTCAE version 5.0, the grade of 0 will be assigned.

Summary statistics of baseline value, observed values and change from baseline at each schedule visit in the continuous hematology and clinical chemistry parameters will be provided by treatment group. Numeric values reported as less than (<) or greater than (>) a laboratory-defined limit will be included with the "<" or ">" signs ignored. Frequency summaries of shifts from baseline grade to the post-baseline grade at each schedule visit, and to the worst post-baseline grade during 12-week treatment period will be provided in the laboratory tests with CTCAE gradings. In addition, frequency summaries of shifts from baseline category to the post-baseline category in terms of normal/abnormal will be provided over time in other laboratory parameters.

Subject data listings of all laboratory data sorted by subject identifier, date of collection and laboratory parameter will be provided based on the safety set, with abnormality indicated.

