9.4. Vital Sign Measurements

Vital sign measures will include sitting systolic and diastolic blood pressures (mmHg), pulse rate (beats/ minute), respiratory rate (breaths/ minute) and oral temperature (°C).

Summary statistics of baseline, observed value and change from baseline will be provided by treatment group over time. Frequency summaries of shift from baseline to post-baseline visits by normal indicator (in terms of low, normal and high) will be provided for pulse rate, respiratory rate and blood pressure. The normal ranges are defined as: 60 to 100 beats/minute for pulse rate, 12 to 20 breaths/minute for respiratory rate, 36.5 to 37.5 °C for oral temperature, 90 to 140 mmHg for systolic blood pressure, and 60 to 90 mmHg for diastolic blood pressure. The low

abnormality is defined as any value lower than the low limit of normal range, and the high abnormality is defined as any value higher than the high limit of normal range.

A subject data listing of all vital signs data will be presented by subject identifier, date of collection and vital sign parameter, with abnormality indicated.

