9.6. Electrocardiogram

Single 12-lead ECGs will be obtained, after the subject has been in the supine position for at least 5 minutes, prior to randomization at Day 1 and at subsequent visit as indicated in the schedule of events. ECG parameters include RR interval, PR interval, QRS width, QT interval, and corrected QT interval from Fridericia's formula (QTcF). In addition, the 12-lead ECG results will be interpreted by the investigator and recorded as: normal; abnormal not clinically significant; or abnormal clinically significant.

Summary statistics of observed values and changes from baseline in ECG parameters will be provided over time. Frequency summaries of shifts from baseline interpretation results to post-baseline interpretation results at each visit will be provided. The number and percentage of subjects who have the following QTcF interval prolongation will be tabulated by treatment group over time. The descriptive summary of QTcF interval for the subjects with each specific interval prolongation will also be presented.

- QTcF > 450 msec
- QTcF > 480 msec
- QTcF > 500 msec

A subject data listing of ECG measurements will be provided by subject identifier, date of collection and ECG parameters.

10. Pharmacokinetic Analysis

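### SAP 9.4 names no worst on-treatment blood-pressure summary and SAP 9.6 no clearly any-time QTcF count, so by-visit rows only bound how many subjects per arm ever crossed a limit

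*SAP*

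**What the plan says.** - **QTcF (SAP 9.6).** For the limits >450, >480 and >500 msec: "The number and percentage of subjects who have the following QTcF interval prolongation will be tabulated by treatment group over time". The next sentence adds: "The descriptive summary of QTcF interval for the subjects with each specific interval prolongation will also be presented". That second sentence gives no time frame. The section also plans by-visit shifts in the investigator's ECG interpretation, and a subject listing.
- **Blood pressure (SAP 9.4).** "Frequency summaries of shift from baseline to post-baseline visits by normal indicator (in terms of low, normal and high) will be provided". High means above 140 mmHg systolic or above 90 mmHg diastolic. All values are listed by subject, with abnormality flagged.
- **Visit rule (SAP 4.2).** "all the by-visit summaries will be based on the nominal visit as collected on the eCRF page", with one exception. If a subject did not complete treatment, the Visit 5 EOT folder is not shown under Week 12 but "will be treated as the treatment early terminated visit". No other visit mapping is done.
- **Laboratory tests (SAP 9.3).** Shifts from baseline grade to each visit are planned, and also "to the worst post-baseline grade during 12-week treatment period will be provided in the laboratory tests with CTCAE gradings".
- **Protocol.** Section 7.7.5 sets out safety summaries by nominal time point. Table 6-1, note c, says: "Any of the procedures may be performed at an unscheduled visit at the discretion of the investigator". Table 3-1 calls for a triplicate repeat ECG when QTcF exceeds 500 ms (women) or 480 ms (men) at any time. Section 6.4.4 promises the number and percentage of subjects with clinically significant laboratory values at any time point. SAP 9.3 names no such table, and SAP 14 records no changes.

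**The concern.** ECGs and vital signs compared with placebo are part of a secondary safety endpoint (protocol 7.2), and cardiovascular effects are a named potential risk (protocol 1.5). The natural per-arm question is how many subjects went over a limit at least once on treatment. The SAP asks that question explicitly of CTCAE-graded laboratory values but not of blood pressure, and for QTcF it leaves the answer to an undated summary.

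Two arms can show identical by-visit rows and still differ in the number of subjects who ever crossed. Some readings also have no named place in a by-visit table: those from early-termination visits, unscheduled visits and repeat ECGs.

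**Working it through.** The documents give no crossing rate and no figure to reproduce. The check is whether the planned rows determine the any-time count.

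**Inputs.** Arm size n = 37 (SAP 4.3). Four on-treatment post-baseline visits: Weeks 2, 4, 8 and 12 (protocol Table 6-1). The by-visit counts are assumed, for illustration only.

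**Formula.** If c_v subjects are over a limit at visit v, the number K who are over it at one or more of the scheduled visits satisfies

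max(c_v) ≤ K ≤ min(n, Σ c_v).

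The lower bound is reached when the same subjects cross each time, the upper bound when they are all different.

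| Crossings at Weeks 2, 4, 8, 12 | Ever over the limit, subjects | Percent of 37 |
|---|---|---|
| 0, 0, 0, 0 | 0 | 0 |
| 1, 0, 0, 0 | 1 | 2.7 |
| 1, 1, 1, 1 | 1 to 4 | 2.7 to 10.8 |
| 2, 2, 2, 2 | 2 to 8 | 5.4 to 21.6 |
| 1, 2, 2, 3 | 3 to 8 | 8.1 to 21.6 |

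For example, 1/37 = 2.7% and 4/37 = 10.8%; 2/37 = 5.4% and 8/37 = 21.6%.

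The count is fixed only when no visit, or a single visit, has crossings. The same argument applies to the blood-pressure shift tables, within each baseline category.

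**Readings outside the rows.** These bounds cover scheduled visits only. A subject whose only crossing was at an early-termination, unscheduled or repeat reading is added to K without appearing in any named row.

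**Baseline.** Protocol 4.1.2 excludes women for QTcF only above 470 ms, so a woman can enter at 451 to 470 ms. A plain count above 450 msec would mix such subjects with new crossings.

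**The case against.** Much can be said for the plan as it stands.

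- **The second QTcF summary may already answer the question.** It carries no by-visit wording, and SAP 4.1 says continuous summaries include the sample size and the maximum. Read that way, it gives an any-time n for each limit. This stands as a plausible reading. It leaves QTcF as an ambiguity, and does nothing for blood pressure.
- **SAP 4.2 reclassifies early-termination readings; it does not discard them.** A reader might infer that they are barred from all tables. The text does not say so: nothing prevents an early-termination row. Subjects who stop drug but stay in the study also return to the regular visit schedule (protocol 4.2.2). What stands is only that no row is named.
- **The adverse event tables cover the important cases.** Clinically significant vital-sign and ECG changes go on the AE page (protocol 6.4.2 and 6.4.3). The hypertension term covers pressure above 160 systolic or 100 diastolic, or any clinically significant rise that changes the antihypertensive regimen (protocol 6.4.5.2). A confirmed QTcF above the action limit interrupts dosing, and a clinically significant rise above 30 ms reduces it (Table 3-1). SAP 9.1 tabulates TEAEs leading to treatment modification or discontinuation by arm. This largely stands. What is left is mainly isolated pressure above 140/90, QTcF above 450 or 480 msec but under the action limit, and unconfirmed crossings.
- **The layout follows protocol 7.7.5 and the listings hold every value.** Both are true. A reader might infer a conflict between protocol and SAP on ECG and vital signs; there is none. The data are not lost either, though a hand count from listings is not a planned per-arm table.

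**Conclusion.** The point holds, as a minor one. For blood pressure, no any-time or worst on-treatment summary is planned. For QTcF, one may be, but the SAP does not say so. For crossings not reported as adverse events, the by-visit rows therefore only bound per-arm incidence once two or more visits have crossings: 1 to 4 of 37 subjects when each of four rows shows one.

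The secure size is the counting bound. It is tempting to say that true any-time incidence would be some multiple of the by-visit figure, but the documents support no such multiple, because it depends entirely on how strongly readings correlate within a subject. With 1 of 37 at each visit, perfect correlation gives 2.7%, the same as the row. Independence gives 1 − (36/37)^4 = 10.4%, or 3.8 times the row. Nothing in the documents says where between these the trial would fall.

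The separate laboratory point also stands. Protocol 6.4.4 promises an any-time table that SAP 9.3 does not name and SAP 14 does not record as dropped. It too is minor, since most such values should also reach the TEAE tables.

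**What to change.** - **SAP 9.4:** add a shift from baseline to the highest on-treatment systolic category and, likewise, diastolic category.
- **SAP 9.6:** add n (%) per arm by maximum on-treatment QTcF category (>450, >480, >500 msec), shown against baseline category. Alternatively, state that the existing descriptive summary is any-time.
- **For both:** use scheduled, unscheduled, repeat and early-termination readings after first dose, with subjects who have at least one post-dose reading as the denominator. Keep the by-visit tables.
- **SAP 9.3:** add the any-time table of clinically significant laboratory values from protocol 6.4.4, or record its removal in SAP 14.

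The cost is some SAP wording and a few table rows from data already collected. Trial conduct and the primary analysis do not change.

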10.1. Pharmacokinetic Data Handling

Plasma concentrations that are below the limit of quantification (BLQ) will be treated as zero for calculation of descriptive statistics and all PK analyses. Missing concentrations will be excluded from all calculations.

All concentrations and PK parameters will be rounded to 3 significant figures for reporting purposes. The only exceptions will be actual sampling times and T_{max} (which will be rounded to 2 decimal places) and the number of data points (which will be reported as integers). Summary statistics will be rounded to the same precision as individual data, with the exception of n (which will be reported as an integer). Estimates and confidence intervals from all statistical comparisons will be reported to 2 decimal places, and associated p-values will be reported to 4 decimal places.

10.2. Plasma Pharmacokinetic Concentrations

Serial blood samples for PK assessment of SKI-O-592, M2, and M4 will be collected from a subset of patients at the following time points:

- Day 1: 0 hour (predose), and at 15 and 30 minutes (± 5 minutes), 1, 2, 4, 8 and 12 hours (± 10 minutes) postdose (12 hour sample should be collected prior to the evening dose).
- Trough: predose samples will be collected pre-morning on Weeks 2 (Day 14), 4 (Day 28), and 8 (Day 56).
- Week 12 (Day 84): 0 hour (predose), and at 15 and 30 minutes (± 5 minutes), 1, 2, 4, 8 and 12 hours (± 10 minutes) after administration.

Individual plasma concentrations of SKI-O-592, M2, and M4 will be presented in data listings and presented graphically versus actual time by treatment and analyte on both linear and semi-logarithmic scales.

Plasma concentrations of SKI-O-592, M2, and M4 will be summarized using descriptive statistics (n , mean, SD, CV, minimum, median, and maximum) by time point for each treatment and day separately. Mean plasma concentrations will be plotted by treatment for each analyte versus nominal time on both linear and semi-logarithmic scales.

10.3. Plasma Pharmacokinetic Parameters

The following plasma PK parameters will, where possible, be estimated on Days 1 and 84 for SKI-O-592, M2, and M4 using actual sampling times via non-compartment analysis using Phoenix WinNonlin version 6.4 or higher:

C_{trough}	Trough concentration observed at steady state (Day 84 only).
C_{max}	Maximum observed concentration.
T_{max}	Time of the maximum observed concentration.

$AUC_{0-\tau}$	Area under the concentration versus time curve within a dosing interval (τ), calculated using the linear trapezoidal rule.
R_{met}	Metabolite ratio, calculated as $[(AUC_{0-\tau} \text{ (metabolite)}) / (AUC_{0-\tau} \text{ (parent)})]$.
R_{AUC}	Accumulation ratio based, calculated as $[AUC_{0-\tau} \text{ (Day 84)} / AUC_{0-\tau} \text{ (Day 1)}]$.
$t_{1/2,eff}$	Effective half-life, calculated as $[\ln(2) / ((-\ln(1 - (1/R_{AUC})) / \tau))]$.

Actual PK blood sampling times will be used for the assessment of all PK parameters. Plasma PK parameters for SKI-O-592, M2, and M4 will be presented in data listings and summarized separately using the following descriptive statistics for each treatment and analyte (n, geometric mean, geometric CV, mean, SD, CV, minimum, median, and maximum). For T_{max} , only n, median, minimum and maximum will be reported.

Note: due to the limited duration of sampling after each dose (i.e. 12 hours), parameters associated with the estimation of a terminal elimination phase (e.g., λ_z , $t_{1/2}$, $AUC_{0-\infty}$, etc.) will not be presented.

10.4. Pharmacokinetic Statistical Analyses

10.4.1. Assessment of Dose-proportionality

A non-linear power model will be used to assess dose-proportionality for SKI-O-592, M2 and M4 on Days 1 and 84 separately. The proportional relationship between the expected value of each parameter [$E(y)$] and dose is written as a power function:

$$E(y) = a * dose^b \text{ [Equation 1]}$$

where 'a' is a constant, 'b' is the proportionality constant and 'y' is the parameter of interest ($AUC_{0-\tau}$ and C_{max}). The exponent, b, will be estimated by performing a linear regression of $\ln(\text{parameter})$ on $\ln(\text{dose})$. The exponent, b, is the estimated slope of the resulting regression line, since taking logs of Equation 1 gives the linear relationship:

$$\ln(y) = \ln(a) + b * \ln(\text{dose}) \text{ [Equation 2]}$$

The relationship is dose proportional when $b = 1$.

To test for lack of fit of the power model, a quadratic term $[\ln(\text{dose})]^2$ will be included in a separate model to test for a systematic departure from linearity; a p-value < 0.05 would indicate significant lack of fit of the power model.

The assumption of a linear relationship between \ln -transformed parameter and \ln -dose will be tested by including a quadratic term $[\ln(\text{dose})]^2$ in the model to test for systematic departures from linearity as a test of lack of fit (LOF) of the power model.

Scatter plots of $AUC_{0-\tau}$ and C_{max} versus dose (on a log-log scale) will be presented by day for all analytes.

10.4.2. Assessment of Accumulation

The accumulation ratio will be estimated by making comparisons of $AUC_{0-\tau}$ and C_{max} on Day 84 with corresponding estimates on Day 1 for each treatment separately; a mixed-effects model will be fitted to log-transformed $AUC_{0-\tau}$ and C_{max} including day (Day 1 or 84) as a fixed effect and subject as a random effect. This model will be used to estimate the accumulation ratio (Day 84 / Day 1) with 95% CIs for each treatment. The geometric least squares means and ratio with 95% CIs will be tabulated by treatment and parameter.

11. Pharmacodynamic Analysis

11.1. Pharmacodynamic Data Handling

Subjects with baseline CD63+ values below the limit of detection will be defined as low responders and excluded from the PD set and all summaries of PD data. Baseline will be defined as the percentage of activated CD63+ cells at predose samples on Day 1.

All PD data will be rounded to 3 significant figures for reporting purposes. The only exceptions will be actual sampling times and TE_{max} (which will be rounded to 2 decimal places). Summary statistics will be rounded to the same precision as individual data, with the exception of n (which will be reported as an integer).

11.2. Pharmacodynamic Data

Serial blood samples for assessment of the percentage of activated CD63+ basophils will be collected in the same subset of patients for whom PK samples will be collected at the following time points:

- Day 1: 0 hour (predose), and at 30 minutes, 1, 2, 4, 8 and 12 hours postdose (12 hour sample should be collected prior to the evening dose).
- Trough: predose samples will be collected pre-morning on Day 14 (Week 2), Day 28 (Week 4), and Day 56 (Week 8).
- Day 84 (Week 12): 0 hour (predose), and at 30 minutes, 1, 2, 4, 8 and 12 hours (± 10 minutes) hours after administration.

Absolute and percentage change from baseline (CFB) in activated CD63+ basophils will be listed by treatment, day and sampling time. Individual change from baseline in CD63+ data will be plotted for each treatment versus time on linear scales using actual times.

Absolute and percentage change from baseline in CD63+ basophils will be summarized by time point for each treatment and day using the following descriptive statistics: n, mean, SD, CV, median, minimum and maximum. Mean percentage change from baseline in CD63+ basophils will be plotted versus time by treatment and day using nominal times on linear scales.

